
The findings of this trial can best be explained by the synergistic effects of tPA and DNase. The fibrinolytic effects of tPA may disrupt fibrinous septations that would otherwise divide the infected collection, allowing DNase to liquefy the thick pus. Similarly, the thinning of pleural fluid by DNase may provide more effective access for tPA to pleural septations.

In summary, a large well-designed trial in adult patients showed that the combination of tPA and DNase therapy improves the drainage of pleural fluid in patients with pleural infection, reduces hospital stay and the need for thoracic surgery. Data for children are lacking at the present time.

Extrapolating from Adult DNase trial to the management of children: The aforementioned review of pediatric pleural empyema suggests that current therapeutic options are still suboptimal. Short-term morbidity persists associated with prolonged hospitalization and pain/discomfort from chest tubes, as well as the need for secondary salvage surgical procedures with potential complications. There may be an additional benefit from the addition of intrapleural DNase to tPA instillation into chest drains. However, extrapolating from adult studies in pleural empyema to children is problematic as pediatric pleural empyema is in many ways a different disease for the following reasons:

- (a) Mortality rates differ substantially. The mortality rate in adults is thought to be 10-20%,^{43 44-46} and comorbidities are common. Most children who develop pleural empyema are otherwise healthy, and mortality is extremely rare in those treated with a drainage procedure. No mortality has been described in pediatric empyema RCTs.^{23,24}
- (b) Epidemiologic trends showing a rising incidence in empyema have been primarily demonstrated in children. Although microbiologic confirmation is often elusive, this does suggest that the microbial etiology of pediatric empyema (e.g. pneumococcal serotypes not covered by conventional vaccines) may differ from adult patients.
- (c) Therapies that have been found to be ineffective in adult patients have been effective in children. For example, intrapleural streptokinase was not found to be beneficial in an adult trial (MIST1 trial),⁴⁶ but was found to be useful for some children in a pediatric trial,⁴⁷ and in a case series.⁴⁸

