Sample size: The primary endpoint is time to hospital discharge after intervention. The mean time to hospital discharge after chest tube insertion and fibrinolytics varies. Published studies with treatment arms that have included chest drain with fibrinolytics as the primary mode of insertion reported hospital days after the intervention from 6 to 15 days.^{23,24} Hospital length of stay tends to be shorter in published RCTs compared with observational studies of empyema, and the most recently published RCT using an identical tPA dosing regimen to that which we are proposing described a mean (SD) stay of 6.8 (2.9) days.³¹ The desired power for the current proposal is 90% to detect a difference of 2 days in the mean time to hospital discharge between the treatment arms. Based on discussions with clinical experts in the field, hospital administrators and parents of children with pleural empyema, it is believed that a 2 day difference between treatment groups is a minimal clinically meaningful difference, and this has been used in previous empyema trials.²⁷ The adult DNase trial found about a 50% difference in length of stay between treatment and placebo groups.⁴²

Sample size was thus calculated assuming a type 1 error rate of 0.05 (2 sided), power (1-β) of 90%, a standard deviation of 2.9 days for each group to detect a difference of 2 days to be 46 per group. Calculations were performed based on a t test of independent groups. While we do not anticipate any post-randomization ineligibility, for example from misdiagnosis, we will increase the sample size by 5% to account for this possibility (total of 49 patients per group). There will be no other adjustment to the sample size requirements due to loss to follow-up for the primary outcome as the primary outcome is assessed in hospital where the research coordinator will be able to ensure complete data collection.

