Blinding: Patients, their parents or other caregivers, site investigators, research assistants and coordinators, treating physicians (pediatricians, radiologists, and interventional radiologists or surgeons), treating nurses, and data managers will be blinded to the treatment allocation. Group allocation will be concealed until the final data analysis is performed. Intervention drugs will be blinded by the research pharmacy. Both arms will be constituted by the research pharmacies in clear liquids in a polyethylene container⁴² in a manner such that both are identical (packaging, colour, volume, texture, and odour) to ensure blinding. After obtaining the treatment number from the central randomization centre, the study pharmacist will retrieve the corresponding vial and one of its treatment number labels will be attached to the patient's case report form (CRF).

Unblinding Procedures: We do not anticipate any circumstances that would require unblinding as knowledge of study arm is not anticipated to affect any treatments for patients.

Data collection methods: Data collection for outcome measures will be mainly collected in hospital by the Research Assistant (RA). At baseline, the following data will be obtained: age, sex, duration of antibiotic treatment prior to chest drainage insertion (days), duration of fever prior to chest drain insertion (days), hypoxia in room air (oxygen saturations less than 92% in room air prior to intervention), microbiologic identification of causative agent (blood culture results, throat swab, pleural fluid culture, pleural fluid PCR), ultrasound of chest: pleural effusion size >10 mm <10 mm, stage of empyema on ultrasound of chest: Stage 1: anechoic nonseptated fluid; Stage 2: echoic fluid without septation; and Stage 3: septated fluid and Stage 4: septations with solid appearing components comprising more than one third of the effusion.⁵³ All ultrasounds will be reviewed by a blinded study radiologist (BC). In addition, patients will receive a follow-up phone call from the RA at 3 months enquiring about any possible readmissions and ongoing symptoms of fever, shortness of breath and/or exercise intolerance.

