Primary outcome: Data will be analyzed according to intention to treat principles for the primary outcome (e.g. patients who do not receive all three doses of study drug will be analyzed in the group they were assigned to). Exceptions to this principle will only include any patient who dies in hospital and will be excluded from the analysis of time to hospital discharge. Given that the primary outcome and other acute secondary outcomes are obtained during hospitalization, it is anticipated that there will be no missing data for these outcomes with the possible, but unlikely exception of in-hospital death, which is rare in childhood empyema. For the follow up outcomes at 3 months, the proportion of patients who follow up will be presented for each treatment arm, and patients who are lost to follow up will be stated but omitted from the analysis. The primary outcome, time (in days) to hospital discharge, will be described as the difference between the two means with the 95% confidence intervals. The student's t-test (independent two sample test assuming equal group size and variance), will be used to detect a difference between the two treatment groups. If the resulting data is inappropriate for a t-test (increasing variance with the mean is the biggest concern since the test is quite robust to non-normality in the population), a suitable transformation or non-parametric test may be used. If feasible, a secondary analysis of the primary outcome will analyze time to discharge, treating death as a competing risk, using methods for survival data. Since randomization is stratified between five centres, the analysis will adjust for this stratification by including centre as a covariate in a multiple linear regression model, to obtain adjusted treatment effects. Additionally, a treatment by centre interaction will be tested to see if the treatment effect differs between centres. Subgroup analyses will also be conducted to explore any potential differences in outcomes by age or sex.

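### Baseline ultrasound stage is collected and centrally read but only tabulated; adding it to the existing centre-adjusted regression would be a nearly free, though modest and uncertain, gain in precision

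*Combined protocol and SAP*

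**What the plan says.** All references are to the combined protocol and SAP.

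- **Eligibility - Inclusion Criteria**, item 2(a), requires the effusion to be documented on chest ultrasound.
- **Data collection methods** lists among the baseline data "ultrasound of chest: pleural effusion size >10 mm <10 mm, stage of empyema on ultrasound of chest". It defines four stages: 1 and 2 are non-septated (anechoic, then echoic), 3 is septated, and 4 has septations with a substantial solid-appearing component. A blinded study radiologist reviews all ultrasounds.
- **Statistical Analysis, Baseline characteristics** shows stage by arm as a frequency. The analysis plan does not use it again.
- **Randomization** is stratified by centre only.
- **Statistical Analysis, Primary outcome** names Student's t-test as the test of the treatment difference. It adds a multiple linear regression with centre as covariate to give adjusted effects, and a treatment-by-centre interaction. It ends: "Subgroup analyses will also be conducted to explore any potential differences in outcomes by age or sex". No rationale, cut-points or test for these subgroups is given there.
- **Secondary outcomes and exploratory outcome** does not use stage.

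**The concern.** The protocol's own account of why the combination should work refers to the state of the pleural collection: "The fibrinolytic effects of tPA may disrupt fibrinous septations that would otherwise divide the infected collection, allowing DNase to liquefy the thick pus". Stage describes that collection, and among the listed baseline variables none is closer to this account. If stage also predicts how long a child stays in hospital, leaving it out of the regression makes the adjusted estimate less precise than the collected data allow.

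Pre-specification matters as well. Stage will be shown by arm in the baseline table. With randomization stratified by centre alone, a visible imbalance is quite possible by chance, and any adjustment for stage chosen after unblinding would be open to challenge. One sentence in the plan removes that difficulty.

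**Working it through.** **1. Reproduce the plan's figure.** Inputs, all from the Sample size section: "assuming a type 1 error rate of 0.05 (2 sided"; "The desired power for the current proposal is 90% to detect a difference of 2 days"; "a standard deviation of 2.9 days for each group to detect a difference of 2 days to be 46 per group". The method named there is an unadjusted two-sample t-test.

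- Normal approximation: n = 2 × (1.960 + 1.282)² × 2.9² / 2² = 44.2, so 45 per group.
- Exact noncentral t: 45 per group gives 89.9% power and 46 gives 90.5%. The stated 46 reproduces.
- Inflation: "we will increase the sample size by 5% to account for this possibility (total of 49 patients per group". 46 × 1.05 = 48.3 and 46 / 0.95 = 48.4; both round up to 49. At 49 per group the power is 92.2%.

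The calculation assumes no covariate gain, so leaving stage out of the model does not make it wrong.

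**2. Precision without stage.** SE = 2.9 × √(2/49) = 0.586 days. The 95% half-width is 1.985 × 0.586 = 1.163 days (t quantile on 96 df).

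**3. Precision with stage.** The half-width is multiplied by √(1 − R²), where R² is the share of variance explained by stage beyond centre. The documents give no value, so a range is assumed. Power is for a 2-day difference with 49 per group and 3 df charged for stage.

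| Assumed R² | Half-width (days) | Reduction | Power, SD 2.9 |
|---|---|---|---|
| 0 | 1.163 | none | 92.2% |
| 0.05 | 1.134 | 0.03 days (about 0.7 h) | 93.4% |
| 0.10 | 1.103 | 0.06 days (about 1.4 h) | 94.5% |
| 0.20 | 1.040 | 0.12 days (about 3 h) | 96.5% |

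The gain is worth more if the SD is larger than planned. With an assumed SD of 3.5 days, power at 49 per group is 79.9% without stage, 83.9% at R² 0.10 and 87.9% at R² 0.20.

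**4. Chance imbalance.** If a share p of children is in stage 3-4, the between-arm difference in that share has SD √(2p(1 − p)/49): 0.101 at p = 0.5 and 0.081 at p = 0.8 (p assumed; not in the documents). The chance of a difference of 10 points or more is about 32% and 22% respectively.

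The effect on the estimate is modest. With stage dichotomised, p = 0.5 and R² = 0.10, the two stage groups differ in stay by 2.9 × √(0.10/0.25) = 1.83 days. A 10-point imbalance then moves the treatment difference by 0.10 × 1.83 = 0.18 days, against an SE of 0.586.

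**5. What a stage subgroup could show.** For stage 1-2 versus 3-4 in 98 children, the interaction SE is 2.9 × √(2/n₁ + 2/n₂), where n₁ and n₂ are the per-arm numbers in the two strata.

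| Assumed split | SE (days) | Power for a 2-day difference in effect | Detectable at 80% power |
|---|---|---|---|
| 50:50 | 1.17 | 39% | 3.3 days |
| 70:30 | 1.28 | 34% | 3.6 days |
| 80:20 | 1.46 | 27% | 4.1 days |

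Each detectable difference exceeds the 2 days that the whole trial is sized to find.

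**The case against.** The strongest reply is that nothing here is an error. The plan adjusts for its only stratification factor, the randomized comparison is valid without stage, and the usual interval already allows for chance imbalance. A reader might infer that the result would be biased, or the trial too small, without stage. The documents support neither.

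Further objections, most of which stand:

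- **Prognostic strength is unknown.** No section relates stage to length of stay. Fever duration, antibiotic duration and hypoxia are also recorded at baseline, and nothing shows that stage predicts better. This is why the gain is a range that starts at nil.
- **The gain is small.** At the planned SD it is one to three hours of half-width, on an outcome reported to 0.1 day, in a trial already above its 90% power target.
- **The named test would not change.** One might read the precision gain as extra patients for the primary analysis. The t-test is the named test, so adding stage to the regression improves only the adjusted estimate.
- **Stage is not a direct marker of DNase's action.** It grades septation and echogenicity. Septations are the target of tPA, which both arms receive; DNase acts on viscosity, which stage does not measure. The link runs only through the proposed synergy. It is therefore tempting, but not supported, to say that a stage subgroup would show where DNase works. The power in step 5 points the same way.
- **Availability is likely but not assured.** The entry criterion requires an effusion seen on ultrasound, not a scan that can be staged, and the timing of the radiologist's reading is not given.

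What survives is narrow: the variable and the regression are both already in the plan, and joining them costs almost nothing.

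**Conclusion.** The point holds as a low-cost improvement, not as the correction of a flaw. Stage is collected and read by a blinded radiologist, then only tabulated, while the regression adjusts for centre alone. Adding it would narrow the adjusted 95% half-width from 1.16 days to between about 1.13 and 1.04 days, if stage explains 5% to 20% of the variance beyond centre. These figures rest on the planned SD of 2.9 days, 49 per arm, a linear model and assumed R² values. If stage is not prognostic, the only cost is one to three degrees of freedom.

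The way effusion size is split at 10 mm, which leaves exactly 10 mm unassigned, is a minor wording matter. The case report form is not among the documents, so it cannot be said that the measurement in millimetres is lost.

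**What to change.** In Statistical Analysis, Primary outcome, before unblinding:

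1. State that the centre-adjusted linear regression also includes the stage read by the blinded study radiologist from the pre-insertion ultrasound. Enter it either as one ordinal term or as three indicators, and choose which in advance. Add a category for scans that cannot be staged.
2. State that the precision gain applies to this adjusted estimate. If the primary inference is meant to benefit, name this model as the primary analysis in place of the t-test; otherwise label it supportive.
3. Optionally, report one treatment-by-stage interaction (1-2 versus 3-4) as an estimate with its interval. Label it exploratory, and note its low power and that stage does not measure viscosity.
4. As a tidy-up, assign an effusion of exactly 10 mm to one of the two size classes.

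The cost is a few sentences and one degree of freedom (ordinal) or three (indicators), plus one more if the category for unstaged scans is used. No extra child, scan or visit is needed, and the sample size stays as it is.

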Primary Hypothesis: Three doses of DNase-tPA, when compared to three doses of tPA via chest drain will reduce the time to discharge after chest drain insertion in children hospitalized with pleural empyema.

Secondary Research Questions: Will there be differences between the groups with respect to other outcomes related to efficacy, cost and safety? The following outcomes will be assessed:

- a) Time to meeting discharge criteria.
- b) Time to drain removal.

Version June 29, 2017.

- c) Duration of fever, defined as the number of days with temperature >38°C.
- d) Need for ventilator support or non-invasive ventilation following intervention.
- e) Risk of serious bleed, defined as intrapleural bleeding resulting in a drop in hemoglobin of greater than 20 g/L or needing a transfusion.
- f) Need for further interventions, defined as the need for further intervention such as placement of another chest drain (by any technique) or surgical intervention such as thoracotomy and decortication, video-assisted thoroscopic surgery, or pneumonectomy.
- g) Hospital readmission related to pleural empyema or its treatment within three months of discharge.
- h) Cost of the hospitalization.
- i) Mortality.
- j) Amount of effusion present at the time of drain removal (exploratory outcome).

Secondary Hypotheses: DNase-tPA, when compared to tPA via chest drain, will:

- a) Reduce the time of fever, time to meeting discharge criteria, time to drain removal and cost.
- b) Not result in an increase in need for ventilator support or non-invasive ventilation following intervention, nor an increase in risk of serious bleed, nor any need for further intervention, nor the risk of hospital readmission, nor the risk of mortality.

TRIAL DESIGN (see Appendix 1 for trial schematic)

Design: The study design will be a superiority randomized controlled trial in a parallel group, 1:1, two arm design.

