- c) *Drain management* - Chest drain management will be at the discretion of treating physicians. Suggested management in the care pathway will include maintaining -20 cm H₂O of continuous suction and once daily flushes with 10 ml of normal saline (on days where no study drug is administered) to maintain patency.
- d) *Criteria for drainage removal* - Similarly, although recommendations for drainage removal will be made in the care map (< 1ml/kg/d), ultimately the decision to remove the chest drain will be made at the discretion of the responsible physician likely based on a gestalt of clinical parameters (amount of drainage, appearance of the child, fever, etc.). All patients will likely be initially on a similar regime of antibiotics and then tailored based on microbiologic results.
- e) *Diagnostic imaging* - There is no consensus on the type (ultrasound versus plain radiograph) or frequency of diagnostic imaging necessary after drain insertion in hospitalized children. Therefore, in contrast to the aforementioned adult RCT of DNase, follow-up radiographs will only be assessed as an exploratory outcome in the study protocol.

Outcomes - Primary outcome: *Time to hospital discharge:* This outcome is the most common outcome measure in trials of childhood empyema. This is defined as the time, measured in hours, and reported in days rounded to a single decimal point, from insertion of the chest drain to discharge from hospital. This will be assessed by a research assistant on a twice daily basis.

Outcomes - Secondary outcomes: Secondary outcomes include measures of effectiveness, harm and cost-effectiveness. Formal clinical follow-up and review of other parameters such as radiographic resolution and lung function testing will not be performed as preliminary work from this group of investigators and others suggests that long-term outcomes in childhood pleural empyema are almost universally positive. Our prospective cohort study has found that by six months, virtually all patients are asymptomatic and follow-up radiographs have normalized in 62/65 (95%) and pulmonary function tests normalize in 27/28 (96%).⁵²

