- a. *Time to meeting discharge criteria:* This is defined as the time, measured in hours, and reported in days rounded to a single decimal point, from insertion of the chest drain to meeting discharge criteria. This will be assessed by a research assistant on a twice daily basis (9 AM and 4 PM) and defined as: no fever (temperature less than 38°C) for 24 hours, normal respiratory rate for age [using the World Health Organization (WHO) age-specific criteria (< 50 breaths/min for 2-12 months, < 40 breaths/min

for 1 to 5 years, and < 20 breaths/min for ≥ 5 years)], no hypoxia (transcutaneous oxygen saturations in room air less than 92%), and drinking fluids well.

b. *Time to drain removal*: This is defined as the time, measured in hours, and reported in days rounded to a single decimal point, from drain insertion to drain removal.

c. *Duration of fever after intervention*: This is defined as the duration, measured in hours, and reported in days rounded to a single decimal point, of fever (defined as temperature $>38^{\circ}\text{C}$ taken by any method) from insertion of the chest drain until resolution. This will be recorded by a research assistant daily.

d. *Need for ventilatory support or non-invasive ventilation following the intervention*.

e. *Serious bleeding*: This is defined as intrapleural bleeding resulting in a drop in hemoglobin of greater than 20 g/L or needing a transfusion.

f. *Need for further interventions*: This is defined as the need for further intervention such as placement of another chest drain (by any technique) or surgical intervention such as thoracotomy and decortication, video-assisted thoroscopic surgery, or pneumonectomy.

g. *Hospital readmission*: Any hospital readmission after discharge from hospital for initial treatment for pleural empyema within three months related to pleural empyema or its treatment (e.g. harm). All hospital readmissions will be categorized as empyema-related or not.

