Secondary outcomes and exploratory outcome: For the secondary and exploratory outcomes that are continuous variables (e.g. duration of drain insertion, hospital stay after intervention to meeting discharge criteria, duration of fever after the intervention, amount of hemithorax occupied by pleural effusion in radiographs) the difference between the two means with the 95% confidence intervals will be presented. The student's t test will be used to detect a difference between the treatment groups. Dichotomous outcomes (serious bleeding, need for further interventions, need for ventilatory support, mortality) will be described as the absolute number and proportion. A Fisher's exact test will be used to detect a significant ($p < 0.05$) difference between the two treatment arms. The treatment effect will also be presented as the relative risk with 95% confidence intervals. These analyses will be viewed as hypothesis generating, and therefore, no correction for multiple testing is planned.

Data Monitoring and Safety: Data monitoring will be conducted with a Data Monitoring Committee (DMC) composed of a pediatric hospitalist, a respiratory physician and an interventional radiologist. The DMC will be completely independent of the investigators, and will be provided with clinical information from the trial case report forms for death, surgical events and adverse events, including those that were described in the adult DNase trial (hemoptysis, gastrointestinal bleeding, chest pain, nausea, transient confusion and rash). The DMC will be able to request additional information from clinicians.

Adverse Event Reporting: All serious unexpected adverse events will be reported to the REB; as per SickKids REB guidelines. All serious adverse drug reactions to the study medication will be reported to Health Canada within 15 calendar days or for death or life-threatening events, within 7 calendar days. In the latter case, a follow-up report will be filed within 8 calendar days. Adverse reactions will be managed according to the standard clinical management practices. All adverse events and adverse reactions will also be reported to the PI within 24 hours.

[figure not shown]
Quality Assurance: This project will be monitored by The Applied Health Research Centre (AHRC) during the data collection phase of the project. The aim is to ensure that all researchers are maintaining

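### For serious bleeding and mortality the relative risk, the only planned between-arm measure, will often have no usable value at 49 per arm, and a non-significant Fisher test cannot support the predicted absence of an increase.

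*Combined protocol and SAP*

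**What the plan says.** Secondary hypothesis (b), under Secondary Hypotheses, predicts that DNase-tPA will "Not result in an increase in need for ventilator support or non-invasive ventilation following intervention, nor an increase in risk of serious bleed", and extends the prediction to further intervention, readmission and death. The section on outcomes notes that "Secondary outcomes include measures of effectiveness, harm and cost-effectiveness", so some of these are safety endpoints.

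The analysis is in Statistical Analysis, under secondary and exploratory outcomes: "Dichotomous outcomes (serious bleeding, need for further interventions, need for ventilatory support, mortality) will be described as the absolute number and proportion". Fisher's "exact test will be used to detect a significant ($p < 0.05$) difference between the two treatment arms", and then "The treatment effect will also be presented as the relative risk with 95% confidence intervals". The paragraph closes with a limit on interpretation: "These analyses will be viewed as hypothesis generating". It names no risk difference, no method for the relative-risk interval and no rule for an arm without events. No margin is attached to hypothesis (b).

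Readmission is defined as a secondary outcome (item g: "All hospital readmissions will be categorized as empyema-related or not") and belongs to hypothesis (b), but it is absent from the list of dichotomous outcomes. The sample size is a "total of 49 patients per group", set by length of stay. No power or precision is given for any harm.

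**The concern.** A ratio needs events in its denominator, and its usual log-based interval needs events in both arms. The background sections suggest that two of the listed outcomes will often not meet this. The protocol cites a 2% prevalence of clinically significant bleeding (Fibrinolytics) and no deaths in earlier pediatric empyema trials (Extrapolating from Adult DNase trial). With 49 per arm, about one bleed per arm is expected (49 × 0.02 = 0.98).

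Hypothesis (b) is also a prediction of no increase, while the only test looks for a difference. A significant excess would contradict (b). A non-significant result is weak evidence for it when the test has little power.

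Safety is one of the three purposes named at the end of the evidence summary. In the adult trial described in the protocol, both intrapleural hemorrhages occurred in the tPA-DNase group. If 2 v 0 were seen here, the relative risk would be infinite, and no planned measure would say how large an excess remains compatible with the data.

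**Working it through.** **Inputs.** n = 49 per arm (Sample size). Bleeding 2% (Fibrinolytics); this is an unpublished one-centre figure for any hemoglobin drop, broader than the endpoint of more than 20 g/L or transfusion, so 1% is also shown. Further intervention 17% to 38% (Deoxyribonuclease section). Mortality: no rate given beyond no deaths in prior pediatric trials; 0.1% is assumed for illustration. No rate is given for ventilation or readmission, so nothing is computed for them.

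**The plan's own figure.** A two-sample t test with difference 2 days, SD 2.9, two-sided 0.05 and 90% power needs 45.17, so 46 per arm (power 90.5%). Adding 5%: 46 × 1.05 = 48.3, so 49. Both figures reproduce.

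**Zero cells.** For rate p, the chance that an arm has no events is q = (1 − p)^49. With equal rates, P(0/0) = q²; P(infinite) = P(estimate of zero) = q(1 − q). With unequal rates, P(any zero cell) = 1 − (1 − q_c)(1 − q_t).

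| Rate, control v DNase-tPA | q_c | q_t | 0/0 | Any zero cell |
|---|---|---|---|---|
| 2% v 2% | 0.372 | 0.372 | 13.8% | 60.5% |
| 1% v 1% | 0.611 | 0.611 | 37.3% | 84.9% |
| 2% v 6% | 0.372 | 0.048 | 1.8% | 40.2% |
| 2% v 10% | 0.372 | 0.006 | 0.2% | 37.5% |
| 17% v 17% | 0.0001 | 0.0001 | under 0.01% | 0.02% |

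At 2% v 2%, q(1 − q) = 0.372 × 0.628 = 23.4%, so 13.8% + 23.4% + 23.4% gives 60.5% after rounding. At the assumed 0.1% mortality, q = 0.952 and 0/0 occurs in 90.7% of trials. When there is a true rise in bleeding, the failures come mainly from a control arm without events.

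**Fisher's test.** All 50 × 50 tables were enumerated with binomial weights, counting two-sided p < 0.05 with more events on DNase-tPA. Significance needs at least 6 v 0 (p = 0.027) or 8 v 1 (p = 0.031).

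| True rates | Detected |
|---|---|
| 2% to 6% | 3.0% |
| 2% to 10% | 18.2% |
| 2% to 20% | 76.6% |
| 17% to 34% | 40.8% |

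A five-fold rise in bleeding, 2% to 10%, would therefore be missed in about 82% of trials.

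**Newcombe risk difference.** With Wilson limits (l, u) for each arm's proportion, the lower limit is d − √[(p_t − l_t)² + (u_c − p_c)²] and the upper limit is d + √[(u_t − p_t)² + (p_c − l_c)²]. For 0/49 the Wilson upper limit is z²/(n + z²) = 3.84/52.84 = 0.073, so 0 v 0 gives ±7.3 points. Other tables (DNase-tPA v control):

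| Events | Difference, points | 95% interval | Fisher p |
|---|---|---|---|
| 1 v 0 | +2.0 | −5.4 to +10.7 | 1.00 |
| 1 v 1 | 0.0 | −8.8 to +8.8 | 1.00 |
| 2 v 0 | +4.1 | −3.8 to +13.7 | 0.49 |
| 5 v 0 | +10.2 | +0.9 to +21.8 | 0.056 |
| 7 v 1 | +12.2 | +1.0 to +24.7 | 0.059 |

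The interval is finite in every table. Exact coverage is 99.8% at 2% v 2%, 97.5% at 2% v 10%, 95.1% at 17% v 34% and 94.3% at 30% v 49%. It excludes zero in the harm direction beside a Fisher p of 0.05 or more in 0.1% of trials at 2% v 2%, 11.3% at 2% v 10% and 8.5% at 17% v 34%. The reverse does not occur.

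**The case against.** A reader might infer that the relative risk is simply not estimable in 61% of trials at the 2% rate. That goes too far. An estimate of zero is finite. The plan names no interval method, and a score interval still gives a one-sided bound when only one arm is empty: 0 v 1 has an upper limit of about 3.8 and 1 v 0 a lower limit of about 0.26. The 61% is the share without a standard log-based interval; only the 14% that are 0/0 have neither an estimate nor an informative bound.

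A reader might also infer that the relative risk should be demoted for every binary outcome. The documents do not support this. At 17% to 38%, further intervention gives an estimable ratio and its limit is power. For ventilation and readmission there is no rate to judge by.

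A third inference would be that the plan intends to claim safety from a non-significant test. Nowhere does it say so. Hypothesis (b) is a prediction, and the analyses are labelled hypothesis generating.

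The other side also notes that counts and proportions are promised, so anyone can compute a risk difference, and that low power for harms is common to trials of this size. Both are true, and they limit the consequence. They do not supply a zero-cell rule or a planned between-arm interval, and they leave (b) without an analysis that could support it.

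**Conclusion.** The concern holds for serious bleeding and mortality. As written, the only planned effect measure has no value in the expected mortality table. At the cited bleeding rate it is 0/0, infinite or zero in 14%, 23% and 23% of trials. Separately, with 18% detection of a rise from 2% to 10%, a non-significant Fisher test cannot support hypothesis (b).

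The bleeding figures assume 49 analysed per arm and the 2% rate. The narrower endpoint could make the true rate lower, which would make zero cells more frequent (85% at 1%). The mortality conclusion rests on the protocol's statement that earlier pediatric trials recorded no deaths.

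The point is minor. The primary analysis is unaffected, the outcomes are secondary and exploratory in status, counts will be shown, and the Data Monitoring Committee receives deaths and adverse events. The missing readmission entry is a clerical gap.

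**What to change.** In the paragraph on secondary and exploratory outcomes:

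- Add the risk difference with a 95% Newcombe interval beside the relative risk for the binary outcomes, and make it the main summary where either arm has no events.
- Keep the relative risk where both arms have events, including for further intervention.
- Keep Fisher's test as the only significance test and call the interval descriptive. Where the interval excludes zero beside a Fisher p of 0.05 or more, report both and claim no significance.
- State that a non-significant test is not evidence of no increase.
- Add readmission to the list, with patients reached at 3 months as the denominator, in line with the plan's handling of loss to follow-up.

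Reword hypothesis (b) as estimation of the risk differences. No margin is then needed.

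The cost is wording and one table column, with no new data or patients. There are three drawbacks. Rare harms will usually read as inconclusive, since even 0 v 0 leaves an upper limit of 7.3 points. The interval and the test will sometimes appear to disagree, as at 5 v 0. Coverage can fall slightly below 95% at higher rates. The low power comes from the sample size and is not changed.
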